**Table 8-1: Historical Control ORRs**

Group Index	Tumor Type	Assumed Control ORR ( $R_g$ )
1	Anal Cancer (squamous cell histology)	15%
2	Biliary Tract Cancer (includes nonresectable disease), intrahepatic or extrahepatic cholangiocarcinoma, gallbladder cancer, and ampullary carcinoma	10%
3	Carcinoid after SSAs (Ki67 < 20%)	7.5%
4	Squamous Cell Cancer of the Cervix (exocervix), Squamous Cell Cancer of the Vagina	20%
5	Endometrial Cancer (after primary treatment including RT). Subjects with tumors > 10% estrogen receptor positive pathology in the primary tumor are excluded.	20%
6	Non-squamous Cell Cancer of the Head and Neck (including Cancer of the Salivary Gland, Adenoid Cystic Carcinoma)	10%
7	Histiocytoses (including Erdheim Chester Disease [macrophage disorder], Langerhans Cell Histiocytosis [LCH, dendritic cell disorder])	15%
8	Lynch Syndrome Associated Cancers (excluding HNPCC)	12.5%
9	Medullary Thyroid Cancer (after TKI [vandetanib or cabozantinib])	20%
10	Merkel Cell Carcinoma (includes unresectable disease)	15%
11	Mesothelioma	10%
12	Nasopharyngeal Carcinoma	17.5%
13	Neuroendocrine Tumors (poorly differentiated, Ki67 > 20%)	10%
14	Neuroendocrine Tumors (well to moderately differentiated) after SSAs or everolimus, including insulinomas	15%
15	Non-Lung Small Cell Carcinoma (includes Small Cell Carcinoma of the ovary of pulmonary or hypercalcemic type)	10%
16	Penile Cancer	15%
17	Rare Women's Cancers: Clear Cell (> 50% clear cell by pathology)	5%
18	Soft-Tissue Sarcoma (including Liposarcoma, Leiomyosarcoma), Malignant	10%

**Table 8-1: Historical Control ORRs**

Group Index	Tumor Type	Assumed Control ORR ( $R_g$ )
19	Peripheral Nerve Sheath Tumor, NF-1	
19	Testicular Cancer (chemotherapy resistant disease or relapsed within 2 years of primary therapy)	10%
20	Thymic Carcinoma or Invasive Thymoma	10%
21	Thyroid Cancer (papillary or follicular), after failing RAI and approved kinase inhibition [lenvatinib]	15%
22	Thyroid Cancer: anaplastic first-line. In BRAF V600e positive subjects, investigators may administer nivolumab after vemurafenib.	5%
23	Uterine Sarcoma (excluding endometrial stromal sarcoma)	15%
24	Vulvar Cancer (post vulvectomy, cisplatin and radiotherapy)	15%
25	Adenoid Cystic Carcinoma	10%

## 8.1 Sample Size Determination

The maximum overall sample size across all tumor groups is 350 subjects. In addition, the maximum permitted sample size per group is 25 subjects, although a group with high posterior probability of success may be permitted a larger sample size at Sponsor discretion. Some groups will enroll more subjects than others. Simulation studies were conducted to evaluate the performance of the analysis under various assumptions for the distribution of true underlying ORRs across the tumor types. Operating characteristics including power and type I error were assessed.

When the treatment effects are similar across all tumor types, estimation efficiencies, due to borrowing, result in strong trial performance. When all groups are in truth effective, the individual groups generally exhibit power between 86.8% and 98.0%, under the scenario of odds ratio improvement of 3. When all groups are ineffective, the individual groups have between a 2.1% and 9.5% chance of mistakenly declaring group success. In addition, the global type I error (proportion of trials that declare at least 1 group successful when none is effective) is controlled at 0.539. Full presentation and discussion of the simulation parameters, corresponding simulation results, and example trials are included in the [Appendix 1](#).

## 8.2 Populations for Analyses

- All enrolled subjects: all subjects who signed an informed consent form and were registered into the IVRS.
- All treated subjects: all subjects who received at least 1 dose of nivolumab.

## **8.3 Endpoints**

### **8.3.1 Primary Endpoint**

ORR is defined as the number of participants with a best overall response of confirmed CR or PR divided by the number of all treated participants. Best overall response is defined as the best response designation, as determined by investigator, recorded between the date of first dose and the date of objectively documented progression per tumor-specific response criteria or the date of subsequent therapy, whichever occurs first. For participants without documented progression or subsequent therapy, all available response designations will contribute to the BOR determination.

### **8.3.2 Secondary Endpoints**

#### **8.3.2.1 Duration of Response**

DOOR is defined as the time from first confirmed response (CR or PR) to the date of the first documented tumor progression as determined by investigator or death due to any cause, whichever occurs first. Participants who start subsequent therapy without a prior reported progression will be censored at the last evaluable tumor assessments prior to initiation of the subsequent anticancer therapy. Participants who die without a reported prior progression will be considered to have progressed on the date of their death. Participants who neither progress nor die will be censored on the date of their last evaluable tumor assessment.

#### **8.3.2.2 TTR**

TTR is defined as the time from first dosing date to the date of the first confirmed response, as assessed by investigator.

#### **8.3.2.3 CBR**

CBR is defined as the number of participants with a best overall response of confirmed CR or PR, or stable disease divided by the number of all treated subjects.

#### **8.3.2.4 Overall survival**

OS is defined as the time from the first dosing date to the date of death. A participant who has not died will be censored at last known date alive. OS rate at 1 year is measured as the survival rate at 1 year from Kaplan-Meier curve of OS.

#### **8.3.2.5 Safety and Tolerability**

Safety and tolerability will be measured by the incidence of deaths, adverse events, serious adverse events, adverse events leading to discontinuation, immune-mediated adverse events, select adverse events, adverse events leading to dose delay, and specific laboratory abnormalities (worst grade) in each tumor group. Toxicities will be graded using the National Cancer Institute (NCI) Common Terminology Criteria for Adverse Events (CTCAE) version 4.0.

[REDACTED]

## 8.4 Analyses

### 8.4.1 Demographics and Baseline Characteristics

Demographics and baseline disease characteristics including age, sex, race, weight, baseline disease diagnosis, and medical condition will be summarized using descriptive statistics by disease type.

### 8.4.2 Efficacy Analyses

The final analysis for each group declares success if the Bayesian posterior probability that the treatment effect in that group (treatment compared to control) is above 80%. Formally:

$$Pr(\theta\pi_g > R_g) > 0.80.$$

DOR, TTR, CBR, and overall survival at 1 year will also be provided for each group.

### 8.4.3 Safety Analyses

Safety analyses will be performed by tumor group in all treated subjects. Descriptive statistics of safety will be presented using NCI CTCAE version 4.0. All AEs, drug-related, AEs, SAEs and drug-related SAEs will be tabulated using worst grade per NCI CTCAE v4.0 criteria by system organ class and MedDRA preferred term. On-study lab parameters including hematology, chemistry, liver function, thyroid function, and renal function will be summarized using worst grade per NCI CTCAE v4.0 criteria.

[REDACTED]

#### **8.4.6      Outcomes Research Analyses**

Not applicable.

#### **8.4.7      Other Analyses**

Not applicable.

### **8.5           Interim Analyses**

**Interim Monitoring** will be conducted, at most, every 4 weeks. At each analysis, the groups will be evaluated for futility and success by comparing posterior quantities for the overall response rate to pre-specified early stopping criteria based on the hierarchical model based on population of subjects with at least 28 weeks of follow-up. The design may limit the maximum number of subjects per group to 25 subjects within the trial. Available resources will be used more effectively by enrolling subjects in groups that offer greater promise of efficacy. Internal assessment of the program will also take into consideration for the final decision of early stopping.

**Early Futility:** If there is a sufficiently low probability (20%) that the ORR in a group exceeds the historical rate  $R_g$  by at least 10%, then the group will stop enrollment early for futility. Formally, enrollment will stop early for futility if:

$$Pr(\pi_g > R_g + 0.10) < 0.20$$

A group is only eligible for early stopping for futility once a minimum of 5 subjects have been evaluated for ORR in that group.

**Early Success:** If there is a sufficiently high probability (95%) that the ORR in a group exceeds the historical rate  $R_g$ , then the group may stop enrollment early for success. Formally, enrollment may stop early for success if:

$$Pr(\pi_g > R_g) > 0.95$$

A group is only eligible for early stopping for success once a minimum of eligible 8 subjects have been evaluated for ORR in that group.

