## **8 STATISTICAL CONSIDERATIONS**

**Overview:** This is a Phase 2 single-arm clinical trial that investigates nivolumab across multiple cancer types. At least 25 tumor types (groups) will be considered. If additional groups are identified in the course of the trial, they will be enrolled and will be included within the statistical analysis provided reasonable estimates of the control response rates can be identified. The trial is designed to estimate the underlying ORR of nivolumab in each tumor type ( $\pi_g$ ). Supporting secondary objectives include the duration of response, TTR, CBR, OS, and safety. All subjects will receive nivolumab.

A hierarchical model that borrows information across tumor subgroups will be used to strengthen the overall evidence within each subgroup. Using the hierarchical model, both continuous monitoring for futility and success will be undertaken throughout the study.

Regularly scheduled trial update analyses occur at most every 4 weeks. At each of these analyses, a Bayesian hierarchical model is fit across the data in all cohorts. For each cohort we determine the Bayesian posterior probability that the treatment effect in that cohort (treatment compared to historical control) is greater than 0 (eg, that treatment is better than control). Formally, if  $\theta_g$  is the true log odds treatment effect for cohort  $g$ , we compute  $Pr(\theta_g > 0 | \text{data})$  for each cohort  $g$ . At the regularly scheduled trial update analyses, each cohort may stop enrollment for success or futility. If a cohort stops enrollment, subjects currently in the cohort are all still followed to their primary endpoint.

Separate final analyses will be conducted for each cohort. A final analysis for a group will occur after enrollment in that group is complete and after all subjects in that group have at least 28 weeks follow-up. Once a group is stopped early for futility, the group will not be re-opened for further enrollment. The final analysis for a cohort declares success if the Bayesian posterior probability that the treatment effect in that cohort (treatment compared to historical control) is above 80%. For example, cohort  $g$  will be declared a success at cohort  $g$ 's final analysis if  $Pr(\theta_g > 0 | \text{data}) > 0.80$ . This posterior probability will incorporate the entire dataset at the time of analysis through the Bayesian Hierarchical Model.

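### Does a futility bar of R_g plus 10 points undercut the odds-ratio-of-3 power statement in the two groups with a 5% control rate?

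*Protocol*

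**What the plan says.** The futility rule uses the same absolute margin in every group: enrollment stops when Pr(π_g > R_g + 0.10) < 0.20, once at least 5 subjects have been evaluated. In Protocol 8.5 the reference is the historical rate exceeded "by at least 10%, then the group will stop enrollment early for futility". SAP 7.5.2.3 has the same rule.

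Table 8-1 gives R_g = 5% to two of the 25 groups: group 17, entered as "Clear Cell (> 50% clear cell by pathology", and group 22, "Thyroid Cancer: anaplastic first-line". The next lowest is group 3 at 7.5%.

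Protocol 8.1 states power on a different scale: "When all groups are in truth effective, the individual groups generally exhibit power between 86.8% and 98.0" per cent, "under the scenario of odds ratio improvement of 3". SAP 5 uses the same scenario with an upper end of 98.4%.

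On what closure means, Protocol 8 says that "each cohort may stop enrollment for success or futility" and that, when one does, "subjects currently in the cohort are all still followed to their primary endpoint". It adds: "A final analysis for a group will occur after enrollment in that group is complete", with 28 weeks of follow-up for all its subjects. The success rule Pr(π_g > R_g) > 0.80 applies to each cohort in Protocol 8, Protocol 8.4.2 and SAP 7.5.2.2.

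**The concern.** An odds-ratio effect and an absolute margin diverge at low control rates. In groups 17 and 22, a drug performing exactly as in the power scenario has a true ORR below the futility reference. Such a cohort could look clearly better than control and still sit near the futility boundary.

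That raises two worries. One is that the quoted power might not hold in these groups. The other is that no single sentence says a futility-closed cohort is still tested at 0.80, so a reader might take closure as the verdict. The second worry could matter a good deal. In one simulation with borrowing under assumed priors, success in these two groups at an odds ratio of 3 was about 99-100% if the final test is kept after closure, and about 48-57% if it is not.

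**Working it through.** **1. The plan's own figure.** The 86.8-98.0% power range comes from simulating a hierarchical model whose priors are in Appendix 1, which is not public. It cannot be reproduced. Three assumed priors (μ is the mean log odds ratio, τ² the between-group variance) were compared with the stated figures:

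| Prior | Group power | Group success under the null | Global error |
|---|---|---|---|
| Stated | 86.8-98.0% | 2.1-9.5% | 0.539 |
| A: μ~N(0,1), τ²~IG(2,1) | 97-99.5% | 2.0-7.3% | 0.52 |
| B: μ~N(0,1), τ²~IG(2,2) | 89-98% | 1.3-7.7% | 0.64 |
| C: μ~N(0,1.8²), τ²~IG(0.5,0.25) | 99-100% | 1.7-6.2% | 0.41 |

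None matches every figure, so the simulated results in step 5 are illustrative.

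**2. Exact arithmetic.** With R_g from Table 8-1, the rate at an odds ratio of 3 is p = 3R/(1 + 2R). At R = 0.05, p = 0.15/1.10 = 13.64%. The reference is 15%, an odds ratio of (0.15/0.85)/(0.05/0.95) = 3.35.

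| R_g | Groups | p at OR 3 | R_g + 10 | Difference (points) |
|---|---|---|---|---|
| 5% | 2 | 13.6% | 15.0% | -1.4 |
| 7.5% | 1 | 19.6% | 17.5% | +2.1 |
| 10% | 9 | 25.0% | 20.0% | +5.0 |
| 12.5% | 1 | 30.0% | 22.5% | +7.5 |
| 15% | 8 | 34.6% | 25.0% | +9.6 |
| 17.5% | 1 | 38.9% | 27.5% | +11.4 |
| 20% | 3 | 42.9% | 30.0% | +12.9 |

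Setting 3R/(1 + 2R) = R + 0.10 gives 2R² - 1.8R + 0.1 = 0, so R = (1.8 - √2.44)/4 = 5.95%. Only groups 17 and 22 lie below it.

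**3. What the crossing does.** Nothing switches at 5.95%, because the rule asks whether a posterior probability is below 0.20. An exact calculation on a cohort's own data (Beta(0.5,0.5) and Beta(1,1) priors, a look after each subject from 5 to 25, early success from 8, true odds ratio 3) gives these closure probabilities:

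- 37-58% at R_g 5%
- 25-43% at 7.5%
- 21-34% at 10%
- 13-16% at 20%

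This is a gradient, and group 3 lies on it without any crossing. Moving the reference in the 5% groups down to 13.6% still leaves closure at 32-49%. Small-sample chance explains much of it.

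**4. What closure does.** Protocol 8 puts four statements in sequence: a cohort may stop enrollment for success or for futility; its subjects are then followed to the endpoint; each cohort has a final analysis once its enrollment is complete; success is a posterior probability above 0.80. The statement that a futility-stopped group is not re-opened falls within this sequence and concerns enrollment only. SAP 7.5.2.3 lists enrollment decisions and final-analysis decisions as separate outputs. Nothing exempts a futility-closed cohort from the test.

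**5. Effect with borrowing.** The simulation used 1,000 trials per setting, all groups at odds ratio 3, 350 subjects over 104 weeks, looks every 4 weeks, the plan's minimum sizes, cap and pause rule, automatic closure, and closed cohorts tested at 0.80. Ranges are over priors A to C:

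- Futility closure: 34-50% in the 5% groups, 3-9% in the 22 groups with R_g of 10% or more.
- Success: 94.1-99.6% against 94.6-99.4%.
- Futility switched off in the two 5% groups: success 94.4-99.5%, mean enrollment 13.2-15.4 instead of 11.4-11.8. The difference is between 13.2 - 11.8 = 1.4 and 15.4 - 11.4 = 4.0 subjects.
- These two groups accruing twice as fast: success 92-100%, mean enrollment 14.2-14.7 against 17.3-19.5 with futility off, a difference of 2.6 to 5.3 subjects.

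**The case for a change.** The best argument for an amendment is that the text leaves a consequential rule to inference. The only readable sentence on what follows a futility stop says that the group stays closed. The trial is open-label with no DMC, Protocol 8.5 lets internal assessment enter the stopping decision, and one sentence would settle the matter at almost no cost. Under priors A to C, 34-44% of trials had a 5% group closed for futility and then declared a success, against 3-5% in groups with R_g of 10% or more. Readers would need help with that result.

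What stands is the arithmetic, the likely direction (these two groups close more often at odds ratio 3), and the absence of one sentence that states the rule outright. The rest is weaker:

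- The reading is not open. Four consecutive statements in Protocol 8 lead to the 0.80 test, and the stated power floor of 86.8% fits that reading better than the 48-57% obtained without the test, although the protocol qualifies its range as holding generally.
- The frequency of a closed cohort succeeding depends on the prior. With almost no borrowing, closure was 58-62% and the final test added only about 11 to 16 points of success, so about 0.105/0.62 = 17% to 0.155/0.58 = 27% of closed cohorts succeeded. On a cohort's own data, no result at 5 to 25 subjects meets both rules at once.
- The 3-9% comparison leaves out group 3, the nearest neighbor.
- The odds ratio of 3 is one simulation scenario, and a minimum gain for continued enrollment need not equal it. Protocol 8.5 gives a purpose for stopping: directing resources to the more promising groups.

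**Conclusion.** No change is needed. In groups 17 and 22 the futility reference exceeds the odds-ratio-of-3 rate by 1.4 points, and that is exact. It contradicts nothing in the plan: closure needs a posterior probability below 0.20, it ends enrollment only, and the cohort is still followed and tested at 0.80. An analyst following Protocol 8 and SAP 7.5.2.2 as written would do this. The rationale for the margin and the per-group stopping probabilities may be in Appendix 1, to which Protocol 8.1 refers for the full simulation results. Their absence from the public text is not a gap in the plan.

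The practical size is a few subjects per cohort (1.4 to 4.0 in the base simulation, 2.6 to 5.3 with doubled accrual), with essentially no change in success in the base simulation. Those figures assume priors A to C and automatic closure. Protocol 8 says a cohort may stop, so actual closure could be lower. With almost no borrowing, closure would cost more, but that model gave group power of about 48-88%, mostly below the stated range, so it does not describe the sponsor's design.

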#### **8.5.1      Pause Rule**

The Bayesian hierarchical model incorporates information from all cohorts into each analysis, however the primary driver of the analysis for each cohort is the data from that specific cohort. Thus, it is important that enough data is available in each cohort where possible. To minimize the possibility of excessive enrollment imbalance between the groups, enrollment may be paused in a cohort at any time where 12 or more patients have enrolled, but have not had, yet, an opportunity to complete their 28 week evaluation visit (dropouts are not included in this calculation if they have no post-baseline tumor assessment). The pause may continue until at least 75% of the subjects in the cohort have reached 28 weeks follow-up or have discontinued due to disease progression.

In addition, based on considerations such as emerging external data, cohorts may be paused by Sponsor decision in consultation with Steering Committee.

## **9 STUDY MANAGEMENT**

### **9.1 Compliance**

#### **9.1.1 *Compliance with the Protocol and Protocol Revisions***

The investigator should not implement any deviation or change to the protocol without prior review and documented approval/favorable opinion of an amendment from the IRB/IEC (and if applicable, also by local health authority) except where necessary to eliminate an immediate hazard(s) to study subjects. If a deviation or change to a protocol is implemented to eliminate an immediate hazard(s) prior to obtaining relevant approval/favorable opinion(s), the deviation or change will be submitted as soon as possible to:

- IRB/IEC
- Regulatory Authority(ies), if applicable by local regulations per national requirements)

Documentation of approval/favorable opinion signed by the chairperson or designee of the IRB(s)/IEC(s) and if applicable, also by local health authority, must be sent to BMS. If an amendment substantially alters the study design or increases the potential risk to the subject: (1) the consent form must be revised and submitted to the IRB(s)/IEC(s) for review and approval/favorable opinion; (2) the revised form must be used to obtain consent from subjects currently enrolled in the study if they are affected by the amendment; and (3) the new form must be used to obtain consent from new subjects prior to enrollment.

If the revision is done via an administrative letter, investigators must inform their IRB(s)/IEC(s).

#### **9.1.2 *Monitoring***

BMS or designee representatives will review data centrally to identify potential issues to determine a schedule of on-site visits for targeted review of study records.

Representatives of BMS must be allowed to visit all study site locations periodically to assess the data quality and study integrity. On site they will review study records and directly compare them with source documents, discuss the conduct of the study with the investigator, and verify that the facilities remain acceptable. Certain CRF pages and/or electronic files may serve as the source documents:

In addition, the study may be evaluated by BMS or designee internal auditors and government inspectors who must be allowed access to CRFs, source documents, other study files, and study facilities. BMS audit reports will be kept confidential.

The investigator must notify BMS promptly of any inspections scheduled by regulatory authorities, and promptly forward copies of inspection reports to BMS or designee.

#### **9.1.2.1 *Source Documentation***

The Investigator is responsible for ensuring that the source data are accurate, legible, contemporaneous, original and attributable, whether the data are hand-written on paper or entered electronically. If source data are created (first entered), modified, maintained, archived, retrieved, or transmitted electronically via computerized systems (and/or any other kind of

electronic devices) as part of regulated clinical trial activities, such systems must be compliant with all applicable laws and regulations governing use of electronic records and/or electronic signatures. Such systems may include, but are not limited to, electronic medical/health records (EMRs/EHRs), adverse event tracking/reporting, protocol required assessments, and/or drug accountability records).

When paper records from such systems are used in place of electronic format to perform regulated activities, such paper records should be certified copies. A certified copy consists of a copy of original information that has been verified, as indicated by a dated signature, as an exact copy having all of the same attributes and information as the original.

